9.7 Interim Analysis

Details of the interim analysis are provided in the appendix I "Interim Analysis".

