10.6 Efficacy Analysis

10.6.1 Primary Efficacy endpoint

Primary Efficacy endpoint will be as follows:

1. Time to resolution of hypoxia

The primary efficacy endpoint is “Time to resolution of hypoxia (Time frame: Up to 28 days)”

This endpoint will be considered to have been met when the patient has attained a score of 4 or lower on the 10-point ordinal scale of clinical status and either of a) or b), (as applicable) and c) is met:

- a) Score is ≤ 4 on consecutive assessments over the next 5 days, if patient continues to remain in hospital (i.e., has not been discharged).

OR

Statistical Analysis Plan
Sponsor: [name], Inc

Study Number: NV-05-983-2020

Version: 2.0 Date: 06JAN2021

- b) Patient was discharged before five consecutive assessments (after reaching a score of 4)

AND

- c) The patient has survived and has not been re-admitted to hospital for COVID-19 management through Day 28.

*Note: Part c) is applicable to patients in both a) and b).
 i.e. Time to resolution of Hypoxia = either "a and c" OR "b and c" is met.*

Time to resolution of hypoxia will be compared between the treatment groups using the Cox proportional hazard model with age, gender, and baseline score on the 10-point ordinal scale of clinical status as covariates. The hazard ratio and its corresponding two-sided 95% confidence interval (CI) and two-sided p -value at 5% level of significance will be obtained from the above Cox proportional hazard model.

As the patients were in the hospital until discharge, missing data in the daily WHO clinical status score were few. To facilitate the definition of the durable response, a very limited and conservative imputation will be implemented to impute a missing clinical status score if adjacent to a valid score on both sides, the imputed score will be the higher (worse) of the two, as discussed in Section 9.5.1.

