Appendix I: Interim Analysis Plan

A single unblinded interim analysis of the primary efficacy endpoint, that is, time to resolution of hypoxia, will be conducted. Resolution of hypoxia is defined as described in Section 10.6.1. This endpoint will be considered to have been met when the patient had attained a score of 4 or lower on the 10-point ordinal scale of clinical status used by the WHO in the SOLIDARITY trial, and either maintained the score of 4 or lower for five consecutive assessments over 5 days or was discharged after reaching the score of 4 or lower. In addition, the patient must also survive and not be readmitted to hospital due to COVID-19 related complications through Day 28 to be considered meeting the endpoint. To be performed when data for time to resolution of hypoxia become available for either the first 390 randomized subjects (50% of the target enrollment) or subjects enrolled by the end of year 2020, whichever is earlier, interim analysis will be conducted for three purposes: 1) Possible early stopping for demonstrated efficacy of the study treatment, 2) Possible early stopping for futility (lack of efficacy), and 3) Sample size reassessment. After reviewing the analysis, the DMC will make a recommendation concerning continuation of the study as planned, termination, or continuation with a larger sample size.

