The interim analysis for efficacy will be performed like the primary efficacy analysis detailed in Section [10.6.1](#) of the Statistical Analysis Plan for the final analysis. Time to resolution of hypoxia will be compared between the treatment groups using the Cox proportional hazard model with age, gender, and baseline score on the 10-point ordinal scale of clinical status as covariates. A Lan-DeMets alpha spending function approach will be adopted in order to maintain the overall Type-I error or alpha at the desired two-sided 0.05 level (Lan & DeMets, 1983). The boundary for possible early stopping for demonstrated efficacy will be determined using a Type I error rate of 0.005 (one-sided); that is, the null hypothesis of zero treatment effect will be rejected if the observed effect is in the direction of treatment benefit and it is significant with one-sided $p < 0.005$. If the trial is not stopped after the interim analysis, the final primary efficacy analysis conducted upon study completion will be based on an adjusted Type I error rate of two-sided 0.04521 (i.e., the result will be considered statistically significant for a Z-statistic ≥ 2.0027).

Assuming the Z-statistic does not reach the boundary for early stopping for demonstrated efficacy, an analysis will be conducted for possible early stopping for futility. A DMC recommendation of early stopping for futility will be based on two factors. The first factor is the conditional power, i.e., the probability of finding a significant beneficial treatment effect with adjusted Type I error rate of two-sided 0.04521 at the end of the study, given the current data and appropriate assumptions about the true treatment effect. The second factor is the estimated effect size from the interim analysis. The DMC may recommend the study be stopped for reasons of futility if either 1) the conditional power is very low (for example, 20% or lower), assuming a hazard ratio equal to the estimated hazard ratio from the current data, or 2) the upper limit of a 95% confidence interval for the difference in median time to resolution of hypoxia is < 1 day. The conditional

Statistical Analysis Plan
Sponsor: [name], Inc

Study Number: NV-05-983-2020

Version: 2.0 Date: 06JAN2021

power will be calculated as in Lachin (2005) and Chen, DeMets, & Lan (2004). Median times to resolution of hypoxia will be estimated by the Kaplan-Meier method.

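### SAP 10.6.1 tests the final primary endpoint at two-sided 5%, while SAP Appendix I requires two-sided 0.04521 for the same test after an efficacy look

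*SAP*

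**What the plan says.** **SAP 10.6.1** compares time to resolution of hypoxia with a Cox model adjusted for age, gender and baseline score on the 10-point scale. The hazard ratio, a two-sided 95% confidence interval and a two-sided p-value "at 5% level of significance will be obtained from the above Cox proportional hazard model". The section mentions neither an interim look nor an adjusted level.

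**SAP Appendix I** plans one unblinded interim analysis of the same endpoint: "The interim analysis for efficacy will be performed like the primary efficacy analysis detailed in Section" 10.6.1. Its aim is "in order to maintain the overall Type-I error or alpha at the desired two-sided 0.05 level". At the look, the null hypothesis "will be rejected if the observed effect is in the direction of treatment benefit" with one-sided p < 0.005. If the trial continues, the final primary analysis "will be based on an adjusted Type I error rate of two-sided 0.04521", which the appendix equates to Z of at least 2.0027.

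**Timing.** The look takes place when endpoint data are available for "the first 390 randomized subjects (50% of the target enrollment) or subjects enrolled by the end of year 2020, whichever is earlier".

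**The link between the two.** SAP 9.7 says only that "Details of the interim analysis are provided in the appendix I". The rule that the SAP overrides the protocol (for example protocol 11.4.2 and 11.8) does not settle a conflict inside the SAP. SAP 9.6 and protocol 11.2 also use 0.05 without adjustment.

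**The concern.** Two sections of one SAP set different levels for the same test on the same endpoint with the same model. Someone programming the final analysis from 10.6.1 would use 5%. Someone who reads Appendix I through to the paragraph on the final analysis would use 0.04521. If the final p-value falls between the two, the claim of success depends on which section is followed, and that choice would be made with the result known.

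The 5% level also does not deliver what Appendix I promises. Part of the error has already been spent at the interim, so a full 5% at the end takes the total above 5%. In addition, the 95% interval in 10.6.1 can exclude a hazard ratio of 1 when Appendix I calls the result not significant.

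**Working it through.** **Inputs**
- Interim efficacy boundary: one-sided 0.005, so a = 2.5758 (Appendix I).
- Final critical value c: 1.96 (10.6.1) or 2.0027 (Appendix I).
- Information fraction t: 0.50 as planned. The values 0.40 and 0.30 are assumptions for an earlier look; the actual fraction is not in the documents.
- 631 events and HR 1.25 (SAP 9.6).

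**Method.** Under the null hypothesis the interim and final statistics (Z1, Z2) are bivariate normal with correlation √t.
- Benefit-direction error = P(Z1 > a) + P(Z1 ≤ a, Z2 > c).
- Total error adds P(Z1 ≤ a, Z2 < −c), because the interim boundary is one-sided and the final test two-sided.

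**Step 1: the plan's own figure.** Setting the benefit-direction error to 0.025 at t = 0.50 gives c = 2.0027, and 2 × P(Z > 2.0027) = 0.04521. Appendix I reproduces exactly.

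**Step 2: the two final levels at t = 0.50**

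| Final c | Interim | Final, benefit | Benefit total | Final, harm | Total |
|---|---|---|---|---|---|
| 1.96 (10.6.1) | 0.500% | 2.228% | 2.728% | 2.500% | 5.228% |
| 2.0027 (Appendix I) | 0.500% | 2.000% | 2.500% | 2.260% | 4.761% |

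(The last line differs from its parts by rounding.) If the interim boundary were symmetric, which it is not, the 1.96 test would give a total of 5.46%.

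**Step 3: an earlier look (assumed fractions)**

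| t | c = 1.96: benefit / total | c = 2.0027: benefit / total | Exact c | Matching CI |
|---|---|---|---|---|
| 0.50 | 2.728% / 5.228% | 2.500% / 4.761% | 2.0027 | 95.48% |
| 0.40 | 2.783% / 5.283% | 2.554% / 4.815% | 2.0134 | 95.59% |
| 0.30 | 2.836% / 5.336% | 2.605% / 4.865% | 2.0235 | 95.70% |

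**Step 4: what it looks like in a report.** With 631 events the standard error of the log hazard ratio is about 2/√631 = 0.0796. Take Z = 1.98:
- p = 0.0477 and HR = exp(1.98 × 0.0796) = 1.17.
- 95% CI = exp(0.1577 ± 1.96 × 0.0796) = 1.002 to 1.368.
- 95.48% CI = exp(0.1577 ± 2.0027 × 0.0796) = 0.998 to 1.373.

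The 10.6.1 interval excludes 1, and the interval that matches Appendix I does not.

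**Step 5: power.** The drift is ln(1.25) × √631 / 2 = 2.803. Counting the interim look at t = 0.50, power is 80.4% with c = 1.96 and 79.2% with c = 2.0027. The smallest significant hazard ratio is exp(2 × 1.96/√631) = 1.169 against exp(2 × 2.0027/√631) = 1.173. At HR 1.25, the probability that the final Z falls between the two thresholds is about 1.2%.

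**The case against.** The best defence is that the SAP already holds the right rule. Appendix I names the final primary analysis, gives its level and states when it counts as significant. It belongs to the same SAP version and is the more specific text. The sentence in 10.6.1 describes output; the same wording recurs for secondary endpoints in 10.6.2, so it can be read as a template line and not as a rival decision rule. Overall alpha is exceeded only if someone ignores the appendix. The excess in the direction of benefit is 0.23 percentage points, and a 95% interval is a legitimate descriptive estimate.

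Much of this stands. Appendix I is probably the intended rule, the number is small, and a 95% interval is not an error in itself. But the 10.6.1 sentence sets a 5% level as well as an interval, in the section that defines the primary analysis. It has no cross-reference, and 9.7 sends the reader to the appendix only for interim details. No sentence says which level governs.

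A second defence is that futility stopping gives error back. If the trial always stopped at conditional power below 20%, the 1.96 test would have a benefit-direction error of about 2.3% at t = 0.50, below 2.5%. However, the wording is "The DMC may recommend the study be stopped for reasons of futility if either" one of two conditions holds, and 20% is offered as an example. A non-binding rule earns no formal credit.

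On early timing, Appendix I adopts a Lan-DeMets approach, which can accommodate an unplanned fraction. The text nevertheless fixes 2.0027 and gives no instruction to recompute it.

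**Conclusion.** The concern holds. The 5% level in 10.6.1 conflicts with Appendix I and, applied after the efficacy look, does not keep the overall two-sided 0.05. At t = 0.50 with the one-sided interim as written, error is 2.73% against 2.5% for benefit and 5.23% against 5% in total. The 2.0027 threshold restores 2.50%. These figures assume the usual bivariate normal approximation and no credit for futility stopping.

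The numerical effect is modest. The point still needs correcting before the Stage I database is locked and unblinded, because it is the success criterion of the only primary test.

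The early-look issue is secondary. At the assumed fractions of 0.40 and 0.30, keeping 2.0027 costs about 0.05 and 0.1 percentage points in the direction of benefit, and total error stays below 5%.

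**What to change.** **SAP 10.6.1.** For the final primary test, replace the 95% interval and the 5% level with a reference to the adjusted final significance level in Appendix I and the matching confidence interval (two-sided 0.04521 and 95.48% if the look was at t = 0.50). If a 95% interval is also shown, label it as descriptive.

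**SAP Appendix I.** After the value 2.0027, add:

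> If the interim analysis is not at 50% information, the final critical value is solved from the observed fraction (primary events at the interim divided by primary events at the final analysis), given one-sided 0.005 spent at the interim, so that the one-sided error is 0.025. If the sample size is increased under this appendix, the denominator is the originally planned number of final events, so that the critical value is fixed before the increase.

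The last sentence was checked at t = 0.50 with c held at 2.0027. The sample size was raised to reach 80% conditional power when conditional power was 50–80% or 20–80%, with the total capped at 1.5 or 2.5 times the plan and no futility credit. Benefit-direction error was 2.45% to 2.48%, so 2.5% is held.

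**Cost.** SAP wording only; the protocol need not change. Power at HR 1.25 and 631 events is 79.2% instead of 80.4%, and the smallest significant hazard ratio is 1.173 instead of 1.169. The threshold is slightly stricter still if the look came early.

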3.1.6.1.2 Study discontinuation procedures

If the patient is discontinued from the clinical study based on criteria mentioned in [Section 3.1.6.1.1](#), the Principal Investigator or a Sub-Investigator is to take appropriate action and conduct the assessments scheduled for Day 28 as specified in [Section 6.3.1.5](#) before the patient is discharged.

The date of discontinuation from the clinical study, the reason for discontinuing the patient from clinical study, and other details are to be investigated. One of applicable reason for discontinuation from the list below will be entered in the eCRF.

When the patient misses the scheduled visits, the Principal Investigator or a Sub-Investigator will confirm the patient's condition using methods such as telephone calls and mail and encourage the patient to visit the site. A follow-up investigation regarding the subsequent course of symptoms, and the presence or absence of AEs, will also be conducted within the scope of the patient's cooperation, and the results will be recorded. When a follow-up investigation is impossible (because of a change of residence or other factors), such situations will also be recorded. A patient will be called 'lost to follow-up' if there is no response from the patient even after 3 documented telephone contact attempts on 3 different days.

Study code: NV-05-983-2020
Protocol No.: CVD-04-CD-001
Sponsor name: [name], Limited
Clinical Study Protocol

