9.1.1.4 Causality Assessment

The relationship between an AE and the study drugs will be determined by the Investigator on the basis of his/her medical/ pharmacological knowledge and clinical judgment and the following definitions:

- **Not Related:** The event is clearly due to extraneous causes (e.g., diseases, environment, etc.) (specify if known) or, the event is most probably produced by other factors such as the patient's clinical state, therapeutic interventions, or concomitant therapy and does not follow a known response pattern to the study product.
- **Possibly Related:** The event is temporally related to study product use but can be explained by another etiology. Information on the effect of study product withdrawal may be lacking.
- **Probably Related:** The event is temporally related to study product use and is consistent with known effects of the study product and/or improves upon withdrawal of the study product.
- **Definitely Related:** The event follows a reasonable temporal sequence from the time of study product administration and/or follows a known response pattern to the study product, and could not have been produced by other factors such as the patient's clinical state, therapeutic intervention, or concomitant therapy, and either occurs immediately following study product administration or improves on stopping the product, or there is a positive reaction at the application site

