11.4 Efficacy Analyses

11.4.1 Primary Efficacy Analyses

Analysis of the primary endpoint:

The time from the start of administration of the study drug to time to *resolution of hypoxia* as described in the [Section 3.1.3.1.1](#) will be compared between the treatment groups using the Cox proportional hazard model with age, gender and disease severity (moderate and severe) as factors and baseline WHO ordinal score at the start of administration of the study drug as baseline covariates. The hazard ratio and its corresponding 95% confidence interval (CI) and p-value will be obtained from the above Cox proportional hazard model; Also Median time, Inter quartile range estimate etc. will be presented and Kaplan-Meier plot will be plotted. All the efficacy analysis mentioned will be performed using ITT and PP population.

For censored patients who died of any cause, discontinued or were lost to follow-up due to treatment-related adverse events or lack of efficacy, they will be censored at Day 28. However, censored patients who discontinued or were lost to follow-up for reasons that were independent of the study medication will be censored at the day of discontinuation of lost to follow-up. Censored patients who were still in the study follow-up at the time of the analysis will be censored at the last day of available follow-up data.

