9.6 Sample Size Calculation

Based on review of published literature, a hazard ratio of 1.25 is reported (adjusted for the stratification in randomization) for time to clinical improvement in COVID-19 patients receiving anti-viral intervention. The hazard ratio of 1.25 is also assumed to be constant throughout the study as per the assumptions of the Cox proportional hazards regression model with the expected average probability of the event over the course of the study to be 0.9 and 0.8 in test and control group respectively. Inequality testing of the hazard ratio using the Cox proportional hazards regression model with 371 subjects in Favipiravir group and 371 subjects in Placebo group achieves 80% power at the 0.05 significance level for an actual hazard ratio of 1.25 assuming the hazard ratio is 1 under the null hypothesis and that the total number of events achieved is 631. Based on the above assumption and considering the dropout rate to be 5%, overall, 390 patients will be randomized in each treatment group. i.e. 780 patients in total to be randomized in the study. The sample size is estimated using nQuery version 8.5.0.0 using Cox proportional hazard regression. Sample size will be re-estimated based on the analysis of results for the primary endpoint observed during interim analyses.

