Necessary steps will be taken to properly manage the situation of informative censoring for patients who did not reach the resolution of hypoxia endpoint. For censored patients who died of any cause, discontinued or were lost to follow-up due to treatment-related adverse events or lack of efficacy, they will be censored at Day 28. However, censored patients who discontinued or were lost to follow-up for reasons that were independent of the study medication will be censored at the day of discontinuation of lost to follow-up. Censored patients who were still in the study follow-up at the time of the analysis will be censored at the last day of available follow-up data.

The above primary endpoint analysis will be done using ITT population

Also, the primary efficacy analysis will be repeated using PP population.

Sensitivity analysis for primary endpoint [12](#):

Three sensitivity analyses are planned.

1. The first is a more relaxed definition of time to resolution of hypoxia. In this analysis, the resolution of hypoxia is defined if subject's clinical status score ≤ 4 is maintained for two consecutive days. The timing of the resolution event will still be the first day when the score falls to 4 or lower. This sensitivity analysis will be done using ITT as described in the primary endpoint.

Statistical Analysis Plan
Sponsor: [name], Inc

Study Number: NV-05-983-2020

Version: 2.0 Date: 06JAN2021

2. The second sensitivity analysis will be based on Kaplan-Meier estimates and log-rank test. Median time to event, along with standard error, percentage of patients achieved resolution of hypoxia, percentage of patients censored, and two-sided p-value obtained using log-rank test at 5% level of significance will be presented for observed case using ITT population.
3. The third sensitivity analysis will be a worst-rank analysis proposed by Lachin (1999). The two treatment groups will be compared by a Wilcoxon-Mann-Whitney test as implemented in SAS PROC NPAR1WAY. Tied ranks will be assigned the midrank. The ranks will be determined as follows:
 - 1) The lowest (best) ranks will be given to patients who meet the primary endpoint definition of treatment success, beginning with the earliest treatment success after beginning of treatment, and survive to Day 28.

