 - 2) The next lowest ranks will be given to patients who do not meet the definition of success but are lost to follow-up or are missing endpoint data for Day 28, but survive to Day 28, beginning with the earliest day for which data are lost for the rest of the study.
 - 3) The next lowest ranks will be given to patients who are informative withdrawals – i.e., they withdraw for a reason related to probable treatment failure – but survive to Day 28, beginning with the withdrawals closest to Day 28 (i.e., the latest withdrawals).
 - 4) The next lowest ranks will be given to patients who are followed to Day 28 but do not meet the primary endpoint definition, beginning with patients with the lowest clinical status score on Day 28.
 - 5) The highest (worst) ranks will be given to patients who die, beginning with the deaths closest to Day 28. Thus, the highest rank will be assigned to the first death.

This sensitivity analysis will be done using ITT population.

Listing will be provided for the 10-point ordinal scale of clinical status and oxygen saturation level.

10.6.2 Secondary Analysis:

All secondary analysis will be done using ITT population.

1. Time to discharge from hospital

Time to discharge from hospital = Date of discharge – Date of randomization +1

Statistical Analysis Plan
Sponsor: [name], Inc

Study Number: NV-05-983-2020

Version: 2.0 Date: 06JAN2021

Time to discharge in days will be summarized descriptively. Time to discharge will be compared between the treatment groups using the Cox proportional hazard model. The hazard ratio and its corresponding two-sided 95% confidence interval (CI) and two sided *p*-value at 5% level of significance will be obtained from the above Cox proportional hazard model; Also Median time, quartile, inter quartile range estimate will be presented.

Patients whose does not discharged up to Day 28 will be right censored as of day 28. Patients who discontinue the study for any reason – withdrawal because of an adverse event or worsening of symptoms, switch to rescue therapy, loss to follow-up, etc. – will be right censored at Day 28.

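### The primary censoring day turns on drug causality, so an unresolved patient leaving for an adverse event graded not related is censored at exit as if uninformative, and exits for worsening COVID-19 have no settled rule

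*SAP*

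**What the plan says.** SAP 10.6.1 undertakes to manage informative censoring, then sets the censoring day of the primary Cox analysis by the cause of leaving. Patients who died, or who "discontinued or were lost to follow-up due to treatment-related adverse events or lack of efficacy, they will be censored at Day 28", form one group; that wording is in Protocol 11.4.1 and SAP 10.6.1 repeats it. In the other group, "censored patients who discontinued or were lost to follow-up for reasons that were independent of the study medication will be censored at the day" they left. Appendix I runs the interim efficacy analysis in the same way as 10.6.1, so the rule also feeds the stopping boundary and the conditional power.

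Three other places bear on how the rule would be applied:

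- Protocol 9.1.1.4 grades an adverse event *Not Related* when, among other grounds, "the event is most probably produced by other factors such as the patient's clinical state".
- Protocol 3.1.6.1.2 calls a patient lost to follow-up "if there is no response from the patient even after 3 documented telephone contact attempts" on three different days.
- SAP 10.6.2, for the secondary endpoints analysed with a Cox model (1, 2, 4, 6 and 8), censors discontinuation for any reason at Day 28 and gives as examples "withdrawal because of an adverse event or worsening of symptoms, switch to rescue therapy, loss to follow-up, etc".

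**The concern.** Whether an exit is informative depends on the patient's prognosis, not on whether the drug caused it. Censoring at exit assumes that the patient would have gone on to resolve like those who stayed. That is doubtful for someone who leaves, still on oxygen, because of a serious complication of COVID-19. Yet such an event can be graded *Not Related* precisely because the disease caused it, and the literal wording then makes the exit independent of study medication.

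Two further classes are left open. Worsening COVID-19 may be called lack of efficacy (Day 28) or an unrelated adverse event (exit day); no definition decides. A patient lost after unanswered calls usually leaves no reason from which a cause can be judged. The primary hazard ratio would then rest partly on causality grading and on coding decisions not yet made.

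**Working it through.** **1. The plan's own figure.** Inputs from SAP 9.6: the design "achieves 80% power at the 0.05 significance level for an actual hazard ratio of 1.25", with 1:1 allocation and a two-sided test.

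- Events = 4(1.960 + 0.8416)² / (ln 1.25)² = 4 × 7.849 / 0.04979 = 630.5, so 631. This matches.
- Evaluable: 631 / 0.85 = 742.4, or 371 per arm. This matches.
- Randomized: 371 × 1.05 = 389.6, or 390 per arm, 780 in all. (Dividing by 0.95 gives 391; the difference is immaterial.)
- Assumed dropouts: 5% of 780 = 39.
- Standard error of the log hazard ratio at 631 events: about 2/√631 = 0.080.

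The censoring rule does not enter this calculation, and the plan gives no figure for its effect.

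**2. The rules side by side, for a patient without resolution.**

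| Reason for leaving | Primary (10.6.1) | Cox secondaries (10.6.2) | Worst-rank sensitivity analysis |
|---|---|---|---|
| Death | Day 28 | Day 28 (any reason) | Worst ranks |
| Adverse event graded related | Day 28 | Day 28 | Informative if probable treatment failure |
| Adverse event graded not related | Exit day | Day 28 | Informative if probable treatment failure |
| Worsening COVID-19 | Not settled | Day 28 | Informative if probable treatment failure |
| Lost, reason unknown | Not settled | Day 28 | Ranked directly after the successes |

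Only the primary analysis uses drug-relatedness.

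**3. Size when worsening exits differ between arms.** Assumptions: treatment-only Cox model on daily data, exponential times, control resolution 0.80 by Day 28, hazard ratio 1.25 among those who stay, exits spread evenly over Days 2 to 8, worsening leavers never resolve.

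- 3% favipiravir, 6% placebo: hazard ratio about 1.30 at Day 28, 1.25 at exit. On the log scale, ln(1.30/1.25) = 0.039, about half of one standard error (0.039/0.080).
- 4% and 8%: about 1.32 at Day 28, 1.25 to 1.26 at exit.

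Here exit-day censoring discards a benefit, so it works against favipiravir.

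**4. Size when only the grading differs.** No true effect, equal adverse-event exits, 75% graded related on favipiravir and 25% on placebo.

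- 5% exits per arm: hazard ratio about 0.96 if the leavers never resolve, 0.97 if they would have resolved like the rest.
- 2.5% exits per arm: about 0.98.

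**5. Outer bound.** No true effect; all 39 assumed dropouts are patients who would not have resolved, leaving on Days 2 to 10. The number of non-resolvers is the same in both arms on average; only the share that leaves differs. 390 per arm, tested at Z = 2.0027 (SAP Appendix I: "adjusted Type I error rate of two-sided 0.04521", so 0.04521/2 = 0.0226 in each direction), 2,000 runs.

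| Exits, favipiravir / placebo | Hazard ratio, exit day | Hazard ratio, Day 28 | Rejects in favour of favipiravir, exit day | Same, Day 28 |
|---|---|---|---|---|
| 5% / 5% | 1.00 | 1.00 | 3.5% | 2.0% |
| 6% / 4% | 1.04 | 1.00 | 7.0% | 1.8% |
| 7% / 3% | 1.08 | 1.00 | 14.3% | 2.6% |
| 8% / 2% | 1.11 | 1.00 | 25.4% | 1.7% |
| 4% / 6% | 0.97 | 1.00 | 1.3% | 1.9% |
| 2% / 8% | 0.89 | 1.00 | 0.1% | 2.2% |

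The direction follows the arm that loses more non-resolvers; a balanced split leaves the estimate at 1.00.

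**The case against.** The strongest reply is that the rule already sends lack of efficacy to Day 28, and worsening of the disease under treatment is naturally read as lack of efficacy whatever the causality box says. A reader might infer that every worsening patient is censored at exit. The documents do not support that; they leave the class unsettled. A reader might also infer, because lack of efficacy is missing from the study discontinuation criteria in Protocol 3.1.6.1.1, that it can never be recorded as a reason. That does not follow either, since those are criteria for discontinuing, and the list of eCRF reasons is not in the text available.

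It is also tempting to argue that known laboratory effects of favipiravir would make related exits commoner in that arm. The protocol weakens this: Grade 3 uric acid or transaminases stop study drug (3.1.6.2.1), and patients who stop drug are encouraged to stay in the study (3.1.6.2.2). Such a stop need not create a censored patient.

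Other mitigation is real. Deaths always go to Day 28. Patients are assessed daily in hospital, so telephone loss mainly concerns those already discharged. The worst-rank analysis separates informative withdrawals by probable treatment failure. Assumed dropout is only 5%, and blinding makes large imbalances less likely.

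What remains: an adverse event graded *Not Related* still goes to the exit day under the literal wording. None of the three sensitivity analyses repeats the primary Cox model under another censoring rule. One relaxes the durability requirement, one is an observed-case log-rank test, and the worst-rank test yields no hazard ratio.

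**Conclusion.** The point holds as a defect in how the primary censoring rule is framed. It sorts exits by drug causality where prognosis matters, leaves worsening and unknown reasons without a rule, and departs from the SAP's own Cox secondaries. It does not show that worsening patients are always censored at exit, or that the result is biased in a known direction.

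Under plausible imbalances within the assumed 5% dropout, the hazard ratio moves by about 0.03 to 0.05: 1.30 against 1.25 for worsening exits of 3% and 6%, or 0.96 to 0.97 instead of 1.00 for 5% exits per arm with 75% against 25% graded related. The latter uses the whole dropout allowance on adverse events, and the grading split is an assumption without a source in the documents. The outer bound shows that concentrated informative exits could matter for the test (14% false rejection at a 7%/3% split), but it assumes that every dropout is a non-resolver and is not a forecast. The rule should be settled before Stage I lock.

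**What to change.** In SAP 10.6.1, and by reference in Appendix I, replace the causality test:

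- Censor at Day 28 every patient without resolution who leaves because of death, any adverse event regardless of causality, or worsening or lack of efficacy. Do the same, whatever the last score, if the reason is unknown or is a withdrawal request with no documented unrelated cause.
- Keep exit-day censoring only for documented administrative reasons. Classify these blind to treatment, before lock, from the reasons already recorded; for exits that enter the interim analysis, do so before that look.
- Add a sensitivity analysis that repeats the primary Cox model with all unresolved discontinuations censored at Day 28, as the secondaries do.

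Make the same change in Protocol 11.4.1 or state the departure in SAP section 11. The cost is a few sentences, one more model run and a blinded review of a few dozen exits (about 39 at the assumed rate). The downside is a slightly more conservative estimate for an arm with more adverse-event exits.
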